3.7.2.1.4 Power calculations ($\alpha=2$, $\beta=1.5$)

For any fixed value of the p_i s, binomial data can be simulated and the results analyzed and examined as to whether the criteria above are met. This will give an estimate of “power” where power is defined as the probability of meeting the criteria under various hypothesized parameter values.

For this section, we assume the sample sizes are two centers each with 12 subjects and 4 centers each with 6 subjects, for a total of $n=48$ subjects in CIT-07.

Preliminary data from CIT centers indicates a rate of favorable outcome between 70% and 90%.

For illustration therefore, suppose that $\pi = 0.70$ and there is no between center variability and so $p_1=p_2=p_3=p_4=p_5=p_6=0.70$. A total of 10,000 data sets were simulated and the proportion where criterion 1 was satisfied was calculated for an estimate of global power, as was the proportion where an individual center satisfied both criterion (a) and criterion (b) for an estimate of the individual center power. The individual power depends on the sample size in each group. The value for a centers with 12 subjects is 0.77 and is denoted as the individual power for a sample of size 12. A second simulation of 10,000 data sets was generated for $\pi = 0.70$ and gave the same result, and therefore 10,000 data sets were generated for other values of π . Results for the global power and the individual center power are given in Table 5.

Table 5 - Power and Size Estimation for $\alpha=2$ and $\beta=1.5$

Probability of Favorable Outcome at Each Center	Global Power	Individual Power (n=12)
0.5	0.03	0.025
0.7	0.84	0.77
0.8	1.00	0.98
0.9	1.00	1.00

The entries in this table can be interpreted as follows. If the true rate is 0.50 or less, there

is an appropriately low probability (0.025 or less) of a center meeting the criteria (corresponding to the concept of size or a type I error). If there is a high rate of favorable outcome, there is a high probability of meeting the criteria (corresponding to power): for a probability of 0.70, there is an individual center power of 77% and for 0.80, an individual center power of 0.98.

The above calculations were done calling WinBUGS from R and sample code is available in Appendix 8.2. Each set of 10,000 simulations takes approximately 12 hours of computer time. The corresponding probabilities that the analysis indicates that the centers with 6 subjects meet criteria 1 and the lower 90% posterior probability bound is greater than 0.45 is 0.02 and 0.66 for true probabilities of 0.50 and 0.70 respectively. These are less than the individual power for the centers enrolling 12 subjects.

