3.7.2.1.5 Additional power calculations

For completeness additional simulations were run assuming different true rates of favorable outcomes at each center. In all cases, $n_1=n_2=12$ and $n_3=n_4=n_5=n_6=6$ was used as the sample size: two centers enrolling 12 subjects and 4 centers enrolling 6 subjects each.

Centers enrolling 6 subjects in CIT-07 and 6 in a different CIT protocol will have an individual power slightly higher than a center enrolling 12 subjects in CIT-07 with the same true probability of favorable outcome, but no more than the Global Power (see SAP section 3.7.2.1.3.1 for the analysis in these cases).

Table 6 - Additional Power Calculations for $\alpha=2$ and $\beta=1.5$ (The final 4 entries in this table were calculated using R2WinBUGS)

N=(12,12,6,6,6,6)	Global Power	Individual Power (n=12)
P=(0.7,0.7,0.7,0.7,0.5,0.5)	0.59	0.56
P=(0.7,0.7,0.7,0.7,0.7,0.5)	0.72	0.68
P=(0.7,0.7,0.7,0.7,0.7,0.3)	0.60	0.56
P=(0.5,0.7,0.7,0.7,0.7,0.7)	0.60	0.31 (center 1) 0.57 (center 2)
P=(0.3,0.7,0.7,0.7,0.7,0.7)	0.29	0.03(center 1) 0.29(center 2)
P=(0.9,0.9,0.9,0.9,0.5,0.5)	1.00	1.00
P=(0.9,0.9,0.9,0.9,0.9,0.5)	1.00	1.00
P=(0.5,0.9,0.9,0.9,0.9,0.9)	1.00	0.40 (center 1) 1.00 (center 2)
P=(0.3,0.9,0.9,0.9,0.9,0.9)	0.99	0.04 (center 1) 0.99 (center 2)

The detailed description of this subgroup analysis plan is provided in SAP Appendix 8.1.

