3.7.6.13 The proportion of subjects receiving a third islet transplant

For each subject, whether the third islet transplant is implemented will be observable at 365 ± 14 days following the initial and final infusion. The true rate of subjects who need a third islet transplant will be analyzed using the method for a binary outcome.

3.7.6.14 Proportion of subjects with HbA1c<7.0% and free of severe hypoglycemic events at each center preparing islets

Rates and 95% exact confidence intervals will be reported for each individual center. Rates will be reported at one year and two years after the final transplant. See subgroup analysis (SAP section 3.7.2.1) for the description of a more in depth analysis that may be

used by the individual centers to support licensure of individual islet preparation laboratories.

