In this example, the 2 centers with low rates of favorable outcome do not impact the ability of the other centers, with higher rates, to meet the criteria.

Example 2: (11,10,3,3,3,3) successes out of (12,12,6,6,6,6), for $\alpha=2$, $\beta=1.5$

	mean	Lower 90% bound
π	0.66	0.52
p_1	0.82	0.69
p_2	0.77	0.63
p_3	0.58	0.38
p_4	0.58	0.38
p_5	0.58	0.38
p_6	0.58	0.38

In the example above it again holds that centers with low success rates do not negatively affect the centers with high success rates meeting the criteria. In the example below, all centers meet the criteria, even the one with 50% favorable outcome rate that does not meet the criteria in the example above. If the favorable outcome rate is high enough at other centers, a center with only 50% favorable outcome rate will meet the criteria.

Example 3: (11,10,5,5,4,3) successes out of (12,12,6,6,6,6), for $\alpha=2$, $\beta=1.5$

	mean	Lower 90% bound
π	0.79	0.68
p_1	0.85	0.75
p_2	0.81	0.69
p_3	0.80	0.65
p_4	0.80	0.65
p_5	0.73	0.56
p_6	0.66	0.46

Alternative Prior Distribution Gamma($\alpha=2$, $\beta=0.75$)

Additional simulations were run assuming different true rates of favorable outcomes at each center for an inverse gamma prior distribution on the between center variance with ($\alpha=2$, $\beta=0.75$).

In all cases, $n_1=n_2=12$ and $n_3=n_4=n_5=n_6=6$: two centers enrolling 12 subjects and 4 centers enrolling 6 subjects. Again, enters enrolling 6 subjects in CIT-07 and 6 in a different CIT study will have an individual power slightly higher than a corresponding center enrolling 12 subjects in CIT-07, but no more than the Global Power.

Table A2 Power and Size for Alternative Prior Distribution ($\alpha=2$, $\beta=0.75$)

Probability of Favorable Outcome at Each Center	Global Power	Individual Power (n=12)
0.5	0.03	0.026
0.7	0.84	0.79
0.8	1.00	0.99
0.9	1.00	1.00

Note that the power and size in A2 are typically slightly higher, than in Table 5 of section 3.7.2.1 but not much higher, consistent with the analysis being robust and stable. In a few cases the probability of a center with a rate of favorable outcome 0.5 or less has a higher probability of meeting the criteria, supporting the choice of $\beta=0.75$ for the analysis. Additional calculations are given in Table A3 below.

Table A3: Additional Power Calculations

N=(12,12,6,6,6,6)	Global Power	Individual Power (n=12)
P=(0.7,0.7,0.7,0.7,0.5,0.5)	0.59	0.57
P=(0.7,0.7,0.7,0.7,0.7,0.5)	0.72	0.68
P=(0.7,0.7,0.7,0.7,0.7,0.3)	0.59	0.56

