P=(0.5,0.7,0.7,0.7,0.7,0.7)	0.59	0.37 (center 1) 0.57 (center 2)
P=(0.3,0.7,0.7,0.7,0.7,0.7)	0.30	0.05 (center 1) 0.29 (center 2)
P=(0.9,0.9,0.9,0.9,0.5,0.5)	1.00	1.00
P=(0.9,0.9,0.9,0.9,0.9,0.5)	1.00	1.00
P=(0.5,0.9,0.9,0.9,0.9,0.9)	1.00	0.58 (center 1) 1.00 (center 2)
P=(0.3,0.9,0.9,0.9,0.9,0.9)	0.99	0.10 (center 1) 0.99 (center 2)

Hypothetical data sets for CIT-07 for $\alpha=2$, $\beta=0.75$

Several hypothetical data sets have been analyzed for illustration.

The table below gives estimates and the lower 90% for the rate of favorable outcome using the alternative prior distribution $\alpha=2$, $\beta=0.75$.

In conclusion it is recommended that for the analysis uses the prior distribution of $\beta=1.5$. A sensitivity analysis to this prior distribution will also be performed on the data from CIT 07.

Example: (11,11,5,2,5,2) successes out of (12,12,6,6,6,6), for $\alpha=2$, $\beta=0.75$

	mean	Lower 90% bound
π	0.74	0.61
p_1	0.84	0.72
p_2	0.83	0.71
p_3	0.77	0.61
p_4	0.55	0.33
p_5	0.77	0.62
p_6	0.55	0.33

Example: (11,10,3,3,3,3) successes out of (12,12,6,6,6,6), for $\alpha=2$, $\beta=0.75$

	mean	Lower 90% bound
π	0.67	0.54
p_1	0.79	0.67
p_2	0.75	0.62
p_3	0.60	0.42
p_4	0.60	0.42
p_5	0.60	0.42
p_6	0.60	0.42

Example: (11,10,5,5,4,3) successes out of (12,12,6,6,6,6), for $\alpha=2$, $\beta=0.75$

	mean	Lower 90% bound
π	0.79	0.69
p_1	0.84	0.74
p_2	0.81	0.70
p_3	0.80	0.66
p_4	0.80	0.66
p_5	0.75	0.60
p_6	0.70	0.52

Comment

The simulations have demonstrated that the planned Bayesian analysis has appropriate power and size properties: centers with a high rate of favorable outcome have an appropriately high probability of meeting the criteria and centers with a low rate of favorable outcome do not. The results of using the alternative prior distribution indicate that the prior distribution will result in stable estimation.

In general the advantage of using the Bayesian model is estimates for each center are more precise than just using the data for each center alone. This is because in the Bayesian model the data from all other centers are incorporated in the estimates for each center through the correlation structure.

References

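### The stated 0.025 pass probability for a centre at 0.50 or less describes only the case where all six centres are at 0.50; the SAP's own tables give 0.31 to 0.58 when the others are at 0.7 or 0.9

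*SAP*

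**What the plan says.** Under SAP 3.7.2.1.3.1 and 3.7.2.1.3.2, a centre with at least 12 subjects must satisfy two criteria. Criterion (a): the pooled one-sided 95% confidence bound excludes 0.50. Criterion (b): the centre's lower 90% posterior bound is at least 0.45. Section 3.7.2.1.3 rests the 12-subject rule on the power calculations.

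Those calculations assume "two centers each with 12 subjects and 4 centers each with 6 subjects". Table 5 gives every centre the same true rate. Interpreting it, 3.7.2.1.4 says that at a true rate of 0.50 or less there "is an appropriately low probability (0.025 or less) of a center meeting the criteria", and likens this to size or a type I error.

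Table 6 in 3.7.2.1.5 lets one centre differ. With centre 1 at 0.5 and the others at 0.7, the individual-power entry reads "0.31 (center 1) 0.57 (center 2"; with the others at 0.9 it reads "0.40 (center 1) 1.00 (center 2".

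Appendix 8.1 repeats these results (Table A1) and adds the alternative prior (Table A3). It remarks after Example 3: "If the favorable outcome rate is high enough at other centers, a center with only 50% favorable outcome rate will meet the criteria". Its closing Comment says that "the planned Bayesian analysis has appropriate power and size properties". Below Table A2 it observes that in a few cases a centre at 0.5 or less "has a higher probability of meeting the criteria, supporting the choice of" beta = 0.75, yet it goes on to recommend beta = 1.5, the value specified in 3.7.2.1.2.

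Section 3.7.6.14 says the analysis may be "used by the individual centers to support licensure of individual islet preparation" laboratories. Section 3.7.2.1 says it does not bear on the study-wide efficacy and safety analyses.

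**The concern.** The sentence is worded as a property of any one centre, but the figure behind it assumes that every centre is equally poor. In that setting the pooled test fails almost every time, and no centre can pass without it. A centre at 0.50 among better ones is a different case: the other centres help to meet criterion (a), and shrinkage pulls the weaker centre's estimate upward. The SAP expects centre rates of 70% to 90%, so this second case is the one in which a weaker centre would be judged.

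What is at stake is the reading of a centre-level pass. Anyone using the result to support licensure of a laboratory, and relying on 2.5%, would understate the chance that a centre at 0.50 passes.

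**Working it through.** **Inputs.** Centre sizes (12,12,6,6,6,6), total 48 (3.7.2.1.4). Criterion (a) needs at least 31 of 48 (2.4). Criterion (b) as above. Model: y_i ~ Bin(n_i, p_i), logit p_i ~ N(mu, 1/tau), mu flat, tau ~ Gamma(2, 1.5), with Gamma(2, 0.75) as the alternative (3.7.2.1.1, 3.7.2.1.2).

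**Formulas.**

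- Pr(a) = Pr(sum of y_i >= 31). With all rates equal to p this is the sum over x = 31 to 48 of C(48,x) p^x (1-p)^(48-x).
- Pr(centre 1 passes) = sum over all (y_1,...,y_6) of the product of the binomial probabilities, times 1{sum y_i >= 31}, times 1{Pr(p_1 > 0.45 | y) > 0.90}. The posterior probability was computed by grid quadrature, and the outcomes were enumerated rather than simulated.

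**Step 1: reproduce Table 5 (beta = 1.5).** Pr(a) is 0.0297 at 0.5 and 0.8359 at 0.7 (SAP: 0.03 and 0.84). The individual probability is 0.0247, 0.769, 0.978 and 0.9995 at 0.5, 0.7, 0.8 and 0.9 (SAP: 0.025, 0.77, 0.98, 1.00). Table 5 reproduces.

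**Step 2: where the 0.025 comes from.** With all centres at 0.50, criterion (b) alone is met with probability 0.170. Requiring (a) as well cuts this to 0.0247. Given that (a) is met, the centre passes with probability 0.0247 / 0.0297 = 0.83. The low figure therefore reflects failure of the pooled test, not control at the centre.

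**Step 3: one weaker 12-subject centre.**

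| Centre 1; others | Pr(a), recomputed | Passes, beta = 1.5: SAP / recomputed | Passes, beta = 0.75: SAP / recomputed |
|---|---|---|---|
| 0.5; 0.5 | 0.030 | 0.025 / 0.025 | 0.026 / 0.025 |
| 0.5; 0.7 | 0.591 | 0.31 / 0.308 | 0.37 / 0.358 |
| 0.5; 0.8 | 0.924 | not given / 0.382 | not given / 0.531 |
| 0.5; 0.9 | 0.999 | 0.40 / 0.387 | 0.58 / 0.594 |
| 0.45; 0.9 | 0.997 | not given / 0.261 | not given / 0.455 |
| 0.40; 0.9 | 0.995 | not given / 0.158 | not given / 0.320 |
| 0.3; 0.7 | 0.299 | 0.03 / 0.029 | 0.05 / 0.046 |
| 0.3; 0.9 | 0.987 | 0.04 (0.05 in Table A1) / 0.039 | 0.10 / 0.111 |

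The largest gap between an SAP entry and the enumeration is 0.014 (0.594 against 0.58).

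**Step 4: size of the gap (beta = 1.5).** At a true 0.50: 0.31 / 0.025 = 12.4 and 0.40 / 0.025 = 16. At a true 0.30: 0.03 / 0.025 = 1.2 and 0.04 / 0.025 = 1.6 (2.0 with Table A1's 0.05).

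**Step 5: the prior sentence.** In all four scenarios with one weak 12-subject centre, beta = 0.75 raises the pass probability: 0.31 to 0.37, 0.40 to 0.58, 0.03 to 0.05, 0.04 to 0.10. That argues for 1.5, so the value named below Table A2 is a slip.

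**The case against.** The strongest reply is that the sentence interprets Table 5, whose row label refers to the rate at each centre, and for that table 0.025 is correct. Nothing is hidden: the unequal-rates results follow in the next subsection and in the appendix, and the remark after Example 3 concedes the effect. This makes the defect a missing qualifier rather than a wrong calculation. It does not remove it. The sentence speaks of a single centre and likens the figure to size, and the Comment repeats the reassurance without limit after Tables A1 and A3 have been shown.

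Other parts of the reply stand and bound the point:

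- Criterion (b) uses 0.45, so a true 0.50 lies above its bar. Calling a pass at 0.50 an error rests on the SAP's own choice of 0.50 or less as the size condition.
- A reader might infer that every poor centre passes more than ten times as often as stated. The tables do not support that: under beta = 1.5 the excess at a true 0.30 is small.
- A reader might infer that criterion (a) is almost always met when only one centre is weak. That holds with the others at about 0.8 to 0.9. With the others at 0.7, Table 6 gives global power of 0.60 and 0.29 for a weak centre at 0.5 and 0.3.
- Example 3 concerns an observed 3 of 6 at a six-subject centre, below the 12-subject threshold. It illustrates shrinkage and says nothing about the pass probability of an evaluable centre.
- The choice of prior is not in doubt: 3.7.2.1.2 and Appendix 8.1 both specify 1.5.

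**Conclusion.** The point holds as an overgeneralised operating characteristic. The 0.025 is right when all six centres are at 0.50. It does not describe a 12-subject centre at a true 0.50 with the others at 0.7 or 0.9, where the SAP reports 0.31 to 0.40 under beta = 1.5 and 0.37 to 0.58 under beta = 0.75. Between 0.30 and 0.50 the probability climbs steeply; with the others at 0.9 and beta = 1.5 it is about 0.16 at 0.40 and 0.26 at 0.45.

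These figures assume CIT-07 alone with sizes (12,12,6,6,6,6). They do not quantify the analysis that pools CIT-02 to CIT-07, whose centre sizes the SAP does not give.

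A reader might go further and conclude that the decision rule must be tightened, or that a pass resting on a shrunken bound should be disallowed. The documents do not require either. The rule already demands criterion (a) as well as (b), and a stricter bar would trade away power, which is a design preference. Nor is the trial's overall efficacy conclusion affected, since 3.7.2.1 separates this subgroup analysis from it. Because the analysis is secondary and the remedy is wording, the point is one that should be fixed rather than a critical one.

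**What to change.** 1. In 3.7.2.1.4, replace the general sentence with: *0.025 if all centres are at 0.50; 0.31 to 0.40 (beta = 1.5) or 0.37 to 0.58 (beta = 0.75) if only the 12-subject centre of interest is at 0.50 and the others are at 0.70 to 0.90, for CIT-07 alone with n = (12,12,6,6,6,6).*
2. Qualify the Comment in Appendix 8.1 in the same way.
3. In the paragraph below Table A2, change the supported value from beta = 0.75 to beta = 1.5.
4. When results are used to support licensure, show each centre's exact one-sided bound, already planned in 3.7.1, beside its Bayesian bound.

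The cost is a few lines of SAP text and one extra column in a results table. No estimate, decision rule or sample size changes. The stated operating characteristic becomes less favourable.

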3.7.2.1.5 Additional power calculations

For completeness additional simulations were run assuming different true rates of favorable outcomes at each center. In all cases, $n_1=n_2=12$ and $n_3=n_4=n_5=n_6=6$ was used as the sample size: two centers enrolling 12 subjects and 4 centers enrolling 6 subjects each.

Centers enrolling 6 subjects in CIT-07 and 6 in a different CIT protocol will have an individual power slightly higher than a center enrolling 12 subjects in CIT-07 with the same true probability of favorable outcome, but no more than the Global Power (see SAP section 3.7.2.1.3.1 for the analysis in these cases).

Table 6 - Additional Power Calculations for $\alpha=2$ and $\beta=1.5$ (The final 4 entries in this table were calculated using R2WinBUGS)

N=(12,12,6,6,6,6)	Global Power	Individual Power (n=12)
P=(0.7,0.7,0.7,0.7,0.5,0.5)	0.59	0.56
P=(0.7,0.7,0.7,0.7,0.7,0.5)	0.72	0.68
P=(0.7,0.7,0.7,0.7,0.7,0.3)	0.60	0.56
P=(0.5,0.7,0.7,0.7,0.7,0.7)	0.60	0.31 (center 1) 0.57 (center 2)
P=(0.3,0.7,0.7,0.7,0.7,0.7)	0.29	0.03(center 1) 0.29(center 2)
P=(0.9,0.9,0.9,0.9,0.5,0.5)	1.00	1.00
P=(0.9,0.9,0.9,0.9,0.9,0.5)	1.00	1.00
P=(0.5,0.9,0.9,0.9,0.9,0.9)	1.00	0.40 (center 1) 1.00 (center 2)
P=(0.3,0.9,0.9,0.9,0.9,0.9)	0.99	0.04 (center 1) 0.99 (center 2)

The detailed description of this subgroup analysis plan is provided in SAP Appendix 8.1.

3.7.3 Analysis of Key Secondary Endpoints

Because this is a single intervention study, the tests will be one sided tests for whether

the true rates are greater than the endpoint’s predetermined “minimum rate for efficacy”. These minimum rates were determined by the investigators to be large enough to have credibility for the islet transplant community. The minimum rate for efficacy is provided in Table 7 for each of the key secondary outcomes.

Table 7: Key Secondary Outcomes and Minimum Rates for Efficacy

	Key Secondary Outcome	Minimum* Rate for Efficacy
1	The proportion of subjects with an HbA1c <7.0% AND free of severe hypoglycemic events from Day 28 to Day 730, inclusive, after the first islet transplant.	50%
2	The proportion of subjects with HbA1c ≤ 6.5% at one year after the first islet transplant AND free of severe hypoglycemic events from Day 28 to Day 365 after the first transplant.	50%
3	The proportion of subjects with HbA1c ≤ 6.5% at two years after the first islet transplant AND free of severe hypoglycemic events from Day 28 to Day 730 after the first transplant.	40%
4	The proportion of subjects free of severe hypoglycemic events from Day 28 to Day 365 after the first islet transplant.	50%
5	The proportion of subjects free of severe hypoglycemic events from Day 28 to Day 730 after the first islet transplant.	40%
6	The proportion of subjects with HbA1c <7.0% at one year after the first islet transplant.	50%
7	The proportion of subjects with HbA1c <7.0% at two years after the first islet transplant.	40%
8	The proportion of subjects with HbA1c ≤6.5% at one year after the first islet transplant.	50%
9	The proportion of subjects with HbA1c ≤6.5% at two years after the first islet transplant.	40%
10	The proportion of insulin-independent subjects at one year after the first islet transplant.	20%
11	The proportion of insulin-independent subjects at two years after the first islet transplant.	10%

As with the primary endpoint, the key secondary endpoints should be available for all transplanted subjects and the analysis will be conducted for the ITT population. If an endpoint is not available for a randomized subject then it will be imputed using the same rules that were used for the primary endpoint.

The observed rate for each key secondary outcome will be used as the point estimate. The analysis will also compute an exact binomial one-sided test for the null hypothesis that the true rate of the outcome is less than or equal to the predetermined minimum rate for efficacy against the alternative that the true rate exceeds the minimum rate for efficacy.

We will use the Benjamini and Hochberg [20] method to account for the multiplicity of the key secondary tests. This method controls the false discovery rate (FDR) rather than the more familiar family-wise error rate (FWER). It provides a powerful approach for identifying those positive tests that are not likely to be true while controlling a reasonable measure of the expected number of false positive tests (the FDR).

The multiple testing procedure considers testing m hypotheses H_1, H_2, \dots, H_m . Each test yields the corresponding p-values P_1, P_2, \dots, P_m . Let $P_{(1)} \leq P_{(2)} \leq \dots \leq P_{(m)}$ be the ordered p-values, and denote $H_{(i)}$ denote the null hypothesis corresponding $P_{(i)}$. The Bonferroni-type multiple testing procedure is defined by the following:

Let q^* the maximum false discovery rate and let k be the largest i for which $P_{(i)} \leq \frac{i}{m} q^*$; then reject all $H_{(i)}$ $i=1, 2, \dots, k$.

For this study there are 11 key secondary endpoints so $m=11$ and we will fix q^* at 0.1.

For each key secondary outcome, the observed rate will be used as the point estimate. The rate and a 95% exact one-sided confidence interval will be reported along with the p-value from an exact one-sided test of the corresponding null hypothesis.

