2.3.2.1 Key secondary endpoints

The target level for HbA1c chosen for this study is 7.0%. This value was chosen because it is the level recommended by the American Diabetes Association and is considered to be the clinically relevant goal for subjects with T1D. A HbA1c level of 6.5% is the goal recommended by the American College of Endocrinology (ACE). We have included achieving a HbA1c level of 6.5%, alone and as a composite with freedom from severe hypoglycemic events at 1 year after the first islet transplant, as **key** secondary endpoints because they correspond to the ACE recommendations and will be of interest to the medical community.

The key secondary endpoints are the following:

- 1) The proportion of subjects with an HbA1c <7.0% AND free of severe hypoglycemic events from Day 28 to Day 730, inclusive, after the first islet transplant.
- 2) The proportion of subjects with HbA1c \leq 6.5% at one year after the first islet transplant AND free of severe hypoglycemic events from Day 28 to Day 365 after the first islet transplant.
- 3) The proportion of subjects with HbA1c \leq 6.5% at two years after the first islet transplant AND free of severe hypoglycemic events from Day 28 to Day 730 after the first islet transplant.
- 4) The proportion of subjects free of severe hypoglycemic events from Day 28 to Day 365 after the first islet transplant.
- 5) The proportion of subjects free of severe hypoglycemic events from Day 28 to Day 730 after the first islet transplant.
- 6) The proportion of subjects with HbA1c <7.0% at one year after the first islet transplant.

- 7) The proportion of subjects with HbA1c <7.0% at two years after the first islet transplant.
- 8) The proportion of subjects with HbA1c \leq 6.5% at one year after the first islet transplant.
- 9) The proportion of subjects with HbA1c \leq 6.5% at two years after the first islet transplant.
- 10) The proportion of insulin-independent subjects at one year after the first islet transplant.
- 11) The proportion of insulin-independent subjects at two years after the first islet transplant.

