3.1 Study Period and Visit Window Definition

3.1.1 Study Period

The trial consists of three periods: (1) the pretransplant period, which includes screening, enrollment, and wait list time; (2) the period that includes the islet transplant procedure(s); and (3) follow-up visits through 24 months following the final transplant. The study period of this trial is a 24-month follow-up after the final islet transplant. Subjects may undergo up to 3 transplants in the course of this study; the final transplant can occur not later than 8 months following the first transplant.

In the first period, individuals who meet the general inclusion criteria will be approached regarding participation in the study. After informed consent has been obtained, they will be formally enrolled into the study. Eligibility will be confirmed based on the results of the screening visit procedure detailed in Appendix 1 of the CIT-07 protocol. Enrolled subjects who meet the eligibility screening for the studies will be put on the waiting list for an islet transplant.

Once a compatible islet preparation becomes available, a subject's eligibility will be re-confirmed and eligible subjects will begin immunosuppression therapy on Day -2 (Day 0 is defined as the day of transplant).

During the post-transplant follow-up period, subjects may receive up to two additional transplants. After receiving his/her initial islet transplant, if a subject does not meet the criteria for insulin independence described in Section 4.1.2 of the CIT-07 protocol, but has either a basal or stimulated C-peptide level ≥ 0.3 ng/mL (0.1 nmol/L), s/he will be considered for a second islet transplant. A second islet transplant will be considered at 75 ± 5 days after the first islet transplant and when all required metabolic assessments are complete. If, after the second islet transplant, both basal and stimulated C-peptide levels remain <0.3 ng/mL (0.1 nmol/L), the recipient will be considered to have failed the endpoint, and immunosuppression will be managed as described in the protocol. A third islet transplant will be considered only if all the criteria described in Section 7.4 of the CIT-07 protocol are met. Islet transplant recipients who have completed 12 months of follow up after their first infusion will no longer be eligible for additional islet transplants under the CIT-07 protocol.

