3.1.2 Visit Windows

The number of visits that occur before the first islet transplant will be determined by time on the waiting list and cannot be determined in advance. Screening tests and baseline measurements that are obtained during this period must be obtained within specified windows relative to the day of randomization, as described in Appendix 1 of the CIT-07 protocol (section 7). Following a transplant, up to 13 visits may be scheduled. Table 4 describes all visits, their scheduled times relative to the islet transplant, and the allowable visit windows.

Table 4 - Study assessment time points and visit windows

Time Points (days relative to transplant)	Visit Number	Visit Window (days relative to transplant)	Equivalent (weeks or months)
Screening	01	N/A	N/A
Waitlist/ Baseline	02	N/A	N/A
0	03	N/A	N/A
3	04	N/A	N/A
7	05	±3	W1
14	06	±3	W2
21	07	±3	W3
28	08	±3	W4
56	09	±7	M2
75	10	±5	M2.5
120	11	±7	M4
150	12	±7	M5
180	13	±7	M6
270	14	±14	M9
365	15	±14	M12

This follow-up schedule will restart with visit 03 on the day that a subsequent islet transplant is performed. There is also a visit scheduled 365 days after the initial transplant. The detailed activities for each scheduled follow-up visit are described in Appendix 1 of the CIT-07 protocol.

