3.7 Efficacy Analyses

3.7.1 Statistical Analysis of Primary Endpoint

HbA1c is the standard measure of glucose control and is used in all major studies as an endpoint for glycemic control. It has been valuable as a risk predictor of diabetes complications. However, since HbA1c is an integrated average, it does not provide information about the range of glucose values a subject experiences. This limitation is a rationale for also including hypoglycemic event occurrence as part of the primary endpoint and various glycemic excursion measures as secondary endpoints.

The primary endpoint for this study is the proportion of subjects with an HbA1c <7.0% at Day 365 AND free of severe hypoglycemic events from Day 28 to Day 365, inclusive, following the first islet transplant, with the day of transplant designated Day 0.

The primary analysis is designed to estimate the true rate of favorable outcomes at one year in subjects in the ITT population pooled over all centers. The proportion of favorable outcomes will be used as the point estimate. An exact one-sided 95% confidence interval will be constructed assuming an underlying binomial distribution for the target population as follows:

If r out of 48 total enrolled subjects achieve the favorable outcome, the exact one-sided 95% confidence interval is given by $p \geq p_L$ where p_L is the solution of the equation

$$0.05 = \sum_{x \geq r} \binom{48}{x} p_L^x (1 - p_L)^{48-x}.$$

0.05 =

The rates of favorable outcome and exact one-sided 95% confidence intervals will be computed for each contributing center.

This analysis will be conducted for the ITT population. The primary endpoint should be available for all treated subjects. An exception will be if a death occurs, if the subject withdraws consent to be followed, or if immunosuppression is begun but the subject never receives a transplant. In these cases the endpoint will be classified as failure to achieve a favorable outcome. Should the endpoint not be evaluated for a particular individual for other reasons, a failure will be imputed unless an evaluation is done at a time longer than one year after transplant, in which case, that later value will be imputed. All imputations will be reported with the primary analysis. The rates and the exact one-sided 95% confidence intervals for complete data and imputed data will be compared to ascertain the sensitivity of the imputation.

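### The one-year imputation threshold is carried unchanged to the two-year key secondary endpoints, so a value from before Day 730 may be counted as a two-year outcome.

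*SAP*

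**What the plan says.** **Endpoints.** Section 2.3.2.1 and Table 7 time the two-year key secondaries from the first transplant, for example "The proportion of subjects with HbA1c <7.0% at two years after the first islet transplant". Endpoints 1, 3, 7, 9 and 11 need HbA1c or insulin status at that point. Endpoint 1 gives no separate date for its HbA1c, but its event window closes at Day 730. Endpoint 5 also runs to Day 730 but needs only event history.

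**Imputation.** Section 3.7.3: "If an endpoint is not available for a randomized subject then it will be imputed using the same rules that were used for the primary" […]. In section 3.7.1, death, withdrawn consent, or immunosuppression without a transplant counts as failure. For any other reason, "a failure will be imputed unless an evaluation is done at a time longer than one year after transplant", and then the later value is used.

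**Visits.** Section 3.1.2: "Table 4 describes all visits, their scheduled times relative to the islet transplant, and the allowable visit windows". The last row of Table 4 is Day 365±14. The section adds "This follow-up schedule will restart with visit 03 on the day that a subsequent islet transplant is performed" and "There is also a visit scheduled 365 days after the initial transplant". Section 3.1.1: "The study period of this trial is a 24-month follow-up after the final islet transplant". Section 3.7.7 plans analyses at 730±14 days after both the initial and the final infusion.

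**The concern.** The later-value exception makes sense for a one-year endpoint, because any evaluation after one year is at least as late as the time point it replaces. With the same threshold on a two-year endpoint, a value can qualify although it is earlier than the time point it is meant to represent. If graft function declines over time, such a value flatters the two-year rate. Imputing failure for everyone without a Day 730 value pulls the rate the other way.

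These endpoints are tested formally. Each has a minimum rate (50% for endpoint 1; 40% for 3, 7 and 9; 10% for 11) and an exact one-sided test, with Benjamini-Hochberg control at q* = 0.1 over 11 endpoints. A choice that the SAP does not settle could therefore decide whether a two-year endpoint is declared met.

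**Working it through.** **1. The test.** No stated figure is in dispute. As a check on the exact one-sided method, P(X ≥ 31 | n = 48, p) is 0.0005, 0.0297, 0.3111, 0.8359 and 0.9962 at p = 0.4, 0.5, 0.6, 0.7 and 0.8, which matches Table 3.

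**2. When re-transplanted subjects are seen, in days after the first transplant.** Inputs from section 3.1.1: a second transplant is considered from 75±5 days, so the earliest is Day 70; the final transplant is at most 8 months after the first, 8 × 365.25/12 ≈ 243 days.

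| Point | Final transplant at Day 70 | Final transplant at about Day 243 |
|---|---|---|
| One year after final (365±14) | 70 + 351 to 70 + 379 = 421 to 449 | 243 + 351 to 243 + 379 = 594 to 622 |
| 24 months after final (730±14) | 70 + 716 to 70 + 744 = 786 to 814 | 243 + 716 to 243 + 744 = 959 to 987 |

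The target window is 730±14, that is Day 716 to 744. Neither range, 421–622 or 786–987, meets it. The only extra visit tied to the first transplant is at Day 365.

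For a subject with one transplant, first and final coincide, so the 24-month point is Day 730 and the schedule fits.

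**3. What the literal threshold admits.** Any value from Day 366 on qualifies. For re-transplanted subjects this includes the Day 421–622 visit, which is 730 − 622 = 108 to 730 − 421 = 309 days early. It also includes a Day 365 visit held late in its window, on Day 366–379. The 24-month value at Day 786–987 qualifies too, and is 56 to 257 days late. The SAP does not rank these values.

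**4. Illustration of what the reading can do.** The following are assumptions, not SAP figures: 14 of 48 subjects (about 30%) lack a Day 730 value; the bar is 40%; the test is one-sided at an unadjusted 5%. The critical value is 26, with P(X ≥ 26 | 48, 0.40) = 0.0328. The count is modelled as Bin(34, p) + Bin(14, p_e), where p is the true two-year rate and p_e the success rate of the substituted values.

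| Handling of the 14 | True two-year rate | P(count ≥ 26) |
|---|---|---|
| All measured at Day 730 | 40% | 0.033 |
| Earlier values, p_e = 50% | 40% | 0.076 |
| Earlier values, p_e = 60% | 40% | 0.15 |
| All measured at Day 730 | 60% | 0.83 |
| All imputed as failure | 60% | 0.03 |

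The expected count moves by 14 × 0.10 = 1.4 to 14 × 0.20 = 2.8 subjects.

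Under Benjamini-Hochberg the per-test cut-off runs from 0.1/11 = 0.0091 to 0.10. Against 40% the critical count is then 25 (tail 0.0604) to 28 (tail 0.0078), depending on rank, so 26 is only a reference value.

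**The case against.** A reader might infer that the SAP schedules no two-year assessment and that it fills the two-year endpoints with earlier values. The text supports neither.

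- **Two-year data are intended.** Section 3.1.1 carries follow-up to 24 months after the final transplant, section 3.7.4 says the key secondaries are measured at one and two years after the initial transplant, and section 3.7.7 names 730±14 days after the initial infusion. Table 4 leaves out even the 24-month follow-up, so it is evidently incomplete, and section 3.1.2 refers to the protocol for visit details. The Day 730 visit may be there. This stands: what is shown is a conflict inside the SAP, not a missing visit.
- **The rule permits early values but does not require them.** Its default is failure, a value after Day 730 also qualifies, and a sensible analyst may move the threshold to two years. This stands as a limit on the claim. It does not remove the defect, because the written threshold is one year and nothing says that it shifts.
- **Single-transplant subjects are largely unaffected.** This stands. For them the gap opens only if the two-year assessment is missed.
- **The endpoints are supportive.** Section 3.7.2 says secondary outcomes are not meant to decide efficacy explicitly. This stands and lowers the severity. The primary endpoint and its Day 365 visit are untouched.

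**Conclusion.** The concern holds as a wrong threshold in a stated rule, together with an inconsistency over the visit schedule. Section 3.7.3 imports a one-year cut-off into endpoints set at two years after the first transplant, and it names neither the reference transplant nor the value to use. Table 4 conflicts with sections 3.1.1, 3.7.4 and 3.7.7 over the Day 730 assessment in re-transplanted subjects.

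The documents do not fix the size. It depends on the share re-transplanted, on how many of them lack a Day 730 value, on the decline in success between the two times, and on the reading chosen. The rise from 0.033 to 0.08–0.15 holds only under the assumptions shown. The day ranges use the 8-month limit. Section 3.1.1 also ends eligibility for further transplants at 12 months, and the two statements need reconciling. If 12 months applied, the one-year-after-final visit could fall as late as about Day 365 + 365 = 730.

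This should be fixed before the two-year analysis. It does not affect the primary conclusion.

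**What to change.** 1. In section 3.7.3, give the two-year endpoints their own rule. A missing endpoint is a failure unless HbA1c or insulin status, as the endpoint requires, was evaluated on or after the opening of the Day 730 window (Day 716) counted from the first transplant. The earliest such value is used, and no value from before that window may be substituted.
2. Reconcile Table 4 with sections 3.1.1, 3.7.4 and 3.7.7 and with the protocol's visit schedule on the Day 730 assessment after the initial transplant. If the protocol already has that visit, only Table 4 needs correcting.
3. Report, for each two-year endpoint, how many outcomes were measured in window, measured late, or imputed as failure.

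Items 1 and 3 cost only SAP wording and one table. Item 2 is editorial unless the protocol also lacks the assessment. The downside is a possibly lower two-year rate where values are truly missing, because an early success could no longer stand in.
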